3.3.1.2 Secondary endpoints

- The proportion of subjects achieving a platelet response any time during the initial dose evaluation period, Week1 through Week 12, Week 1 through Week 16, Week 1 through Week 24, and Week 1 through Week 52.
- The proportion of subjects who become platelet transfusion independent during the initial dose evaluation period, Week1 through Week 12, Week 1 through Week 16, Week 1 through Week 24, Week 1 through Week 52, Week 1 through Week 104, and Week1 through Week 156
- The proportion of subjects achieving erythroid response and/or neutrophil response during the initial dose evaluation period, Week1 through Week 12, Week 1 through Week 16, Week 1 through Week 24, Week 1 through Week 52, Week 1 through Week 104, and Week1 through Week 156
- Duration of platelet response
- Time to platelet response
- Changes in platelet count, hemoglobin concentration, and neutrophil count as continuous variables
- Changes in bone marrow cellularity and reticulin grade
- Changes in GIMEMA bleeding scale
- The proportion of subjects achieving tri-lineage responses
- The proportion of subjects able to discontinue study drugs after achieving normal level for 8 consecutive weeks without transfusion.
- Duration of study drug discontinuation while maintaining stable response

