5.4 Criteria for entering long-term treatment period

- 1) Subjects with platelet responses confirmed during 8 weeks prior to Week 53 (Week 46-Week 53)
- 2) Subjects who do not have any significant changes in medical condition during the initial evaluation period and extension period (Week 1-Week 52) including bone marrow stem cell disorders or new active malignancies

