6.2.3 Recording concomitant medication and therapy in electronic Case Report Form (eCRF)

All concomitant medication and therapy that a subject received during the period after enrollment through to the end of the study will be recorded on electronic case report form (eCRF) by the investigator with the following information for each concomitant medication and therapy: name of drug, route of administration, duration of treatment and justification for the administration. Agents not intended for medical treatment such as rehydration including saline solution, dissolving solution, or contrast medium for imaging diagnostics are not required to be recorded.

Platelet transfusions given between the period within 56 days (Day -55) prior to the first administration of AMG531 (Day 1) and RBC transfusion given between the period of within 26 weeks (Day -181) prior to the first administration of AMG531 (Day 1) through to the end of study will be recorded in eCRF, including date of each transfusion, volume of transfusion (unit and mL), platelet count or hemoglobin concentration before each transfusion, and reason for each transfusion.

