12 STATISTICAL ANALYSIS

12.1 Statistical methods

Generally, categorical variables will be summarized by the number of subjects and the percentage of subjects in each category to the total number of subjects, and continuous variables will be summarized by descriptive statistics (number of subjects, mean, standard deviation, median, minimum, and maximum). Coefficient of variation and geometric mean will be also presented to summarize pharmacokinetic parameters.

Data will be cut off, collected and analyzed when all subjects complete the observations at week 17.

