12.1.1 Efficacy

Platelet count measured within 7 days after platelet transfusion will not be subjected to the efficacy assessment. Likewise, hemoglobin concentrations determined within 28 days after RBC transfusion will not be subjected to the efficacy assessment. Neutrophil counts determined within 7 days of G-CSF as a rescue medication will not be used for the efficacy assessment.

Platelet count, hemoglobin concentrations and neutrophil counts determined in occasions other than in the scheduled visit in this study, including ordinary medical examinations and follow-up, will not be used for efficacy assessment.

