12.1.1.2 Secondary endpoint

The secondary endpoint will be evaluated based on the PPS. The proportion of subjects with a platelet response in any time during the initial dose evaluation period, Week 1 through Week 12, Week 1 through Week 16, Week 1 through Week 24, and Week 1 through Week 52 or the proportion of subjects achieving platelet transfusion independency during the initial dose evaluation period, Week 1 through Week 12, Week 1 through Week 16, Week 1 through Week 24, Week 1 through Week 52, Week 1 through Week 104, and Week 1 through Week 156 will be calculated in the same manner as the primary variables. Platelet transfusion independence is defined as achieving transfusion free period of at least 8 consecutive weeks.

The proportion of subjects with erythroid and/or neutrophil response during the initial dose evaluation period as well as in Week 1 through Week 12, Week 1 through Week 16, Week 1 through Week 24, Week 1 through Week 52, Week 1 through Week 104, and in

Week1 through Week 156 will be calculated in the same manner as the primary variables. An erythroid response is defined as achieving an increase in hemoglobin concentration of ≥ 1.5 g/dL above baseline without transfusion or reduction in the transfusion unit by at least 4 units for 8 consecutive weeks compared with the pretreatment transfusion requirement in the previous 8 weeks prior to the first administration of AMG531 (Day -55 to Day 1). A neutrophil response is defined in those with ANC of $< 0.5 \times 10^9/L$ as a 100% increase over the baseline, or an increase in ANC of $> 0.5 \times 10^9/L$ in subjects with a pretreatment ANC of $< 1.0 \times 10^9/L$.

Time to platelet response and duration of platelet response will be summarized.

The change in platelet counts, hemoglobin concentrations, and neutrophil counts from baseline will be summarized at each scheduled visit. For the transfusion, only the platelet transfusion given due to platelet count of $< 10 \times 10^9/L$ (prophylactic transfusion) or due to bleeding (therapeutic transfusion) and RBC transfusions of which hemoglobin concentration is ≤ 9.0 g/dL or due to symptomatic anemia will be included in the response assessment.

The changes in bone marrow cellularity and reticulin grade will be summarized by each subject based on the test reports. The changes in the GIMEMA bleeding scale will be summarized.

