12.4 Handling of missing, unused, and abnormal data

Any missing data on platelet, hemoglobin, and neutrophil for evaluating efficacy response will be handled as a missing value and will not be imputed with an alternative value using a statistical approach.

If data from a particular subject needs to be examined how to handle them because of an event unexpected at the start of the study, how to treat such data will be decided before database lock.

12.5 Development of the statistical analysis plan and procedure for reporting deviations from the original statistical analysis plan

The detailed statistical analysis plan including the analyses described in this section will be finalized before database lock. Any major change to the statistical analysis plan will be described in the clinical study report.

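### Per-visit change in platelets and hemoglobin omits post-transfusion values with nothing in their place, so mean improvement will tend to be overstated, most clearly for hemoglobin

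*Combined protocol and SAP*

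**What the plan says.** Section 3.3.1.2 lists as a secondary endpoint "Changes in platelet count, hemoglobin concentration, and neutrophil count as continuous variables". Section 12.1.1.2 gives the analysis: "The change in platelet counts, hemoglobin concentrations, and neutrophil counts from baseline will be summarized at each scheduled visit". Under section 12.1 this means number of subjects, mean, standard deviation, median, minimum and maximum. No model is planned.

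Three rules decide which values enter:

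- Section 12.1.1, platelets: "Platelet count measured within 7 days after platelet transfusion will not be subjected to the efficacy assessment".
- Section 12.1.1, hemoglobin: "hemoglobin concentrations determined within 28 days after RBC transfusion will not be subjected to the efficacy assessment". The same section also bars counts taken outside scheduled visits.
- Section 12.4: missing platelet, hemoglobin and neutrophil data "will be handled as a missing value and will not be imputed with an alternative value using a statistical approach".

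The Definition of Terms ties platelet transfusion to a count below 10 × 10⁹/L or to bleeding, and red-cell transfusion to hemoglobin of 9.0 g/dL or less or to symptomatic anemia. For each transfusion, section 6.2.3 has the eCRF record the "platelet count or hemoglobin concentration before each transfusion, and reason for each transfusion". Section 12.1.1.2 evaluates the secondary endpoints on the PPS and repeats the calculation in the same way on the FAS.

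**The concern.** Whether a value is excluded depends on the outcome itself. A subject whose counts stay low is transfused, and the following platelet or hemoglobin values leave the summary. A subject whose counts recover is not transfused and stays in. The mean change at a visit therefore describes a group tilted towards those doing well, and the tilt varies from visit to visit with transfusion timing.

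Nothing else in the plan covers this endpoint. The rule in section 6.1.2 that treats a week without a platelet measurement because of transfusion as a non-response concerns platelet response, not the continuous change. The FAS analysis applies the same exclusions.

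Later visits are selected further. Section 11.1.1 withdraws subjects with no platelet response after 8 weeks at the top dose. Entry to the long-term period is limited by section 5.4 to "Subjects with platelet responses confirmed during 8 weeks prior to Week 53", and failing that criterion is itself a withdrawal reason.

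The trial is meant to support a recommended initial dose with 8 subjects per arm, so losing two or three subjects from a visit can move an arm mean noticeably.

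**Working it through.** The documents give no expected change, SD, response rate or transfusion frequency, so there is no planned figure to reproduce. The checks below establish mechanism and direction. Their sizes rest on stated assumptions.

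**1. Share of weekly visits that remain usable.** Inputs: weekly hematology (sections 8.2.2 to 8.2.4) and windows W of 7 and 28 days (section 12.1.1). Assumption: a transfusion every T days, given just after a scheduled draw. The visits then fall 7, 14, …, T days after the last transfusion, and the usable share is the number of these beyond W, divided by T/7. The plan does not say whether day W is inside the window, so both readings are shown.

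| Interval T | Platelets, day 7 inside / outside | Hemoglobin, day 28 inside / outside |
|---|---|---|
| 7 days | 0% / 100% | 0% / 0% |
| 14 days | 50% / 100% | 0% / 0% |
| 28 days | 75% / 100% | 0% / 25% |
| 35 days | 80% / 100% | 20% / 40% |
| 56 days | 87.5% / 100% | 50% / 62.5% |

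For platelets the loss is partial. A count drawn before a same-day transfusion is kept unless an earlier window still covers it, and much depends on day 7. For hemoglobin the result is robust: at intervals shorter than 28 days nothing is usable on either reading, and at exactly 28 days the share is 0% or 25%.

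**2. Effect on an arm mean.** Arm size 8 (section 3.5.1). Assume r responders each change by D, the others change by 0, and k of the others are excluded. The all-subject mean is rD/8 and the summarized mean is rD/(8 − k). With r = 4:

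| | All 8 | k = 1 | k = 2 | k = 3 | k = 4 |
|---|---|---|---|---|---|
| Platelets, D = 20 × 10⁹/L | 10.0 | 11.4 | 13.3 | 16.0 | 20.0 |
| Hemoglobin, D = 1.5 g/dL | 0.75 | 0.86 | 1.00 | 1.20 | 1.50 |

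The overstatement is 8/(8 − k) − 1, or 14%, 33%, 60% and 100%.

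**3. Simulation with the documents' windows** (40,000 subjects per scenario, days 7 and 28 counted as inside). For platelets at Week 9 it used the documents' count trigger and assumed a responder gain of 25 × 10⁹/L, a transfusion increment of 10 or 20 with a 2-day half-life, and counts checked once or twice a week. For hemoglobin at about Week 25 it assumed a responder gain of 2.5 g/dL and a transfusion increment of 2 g/dL fading over 42 days.

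| Assumed responder share | True mean change | Mean of usable values | Overstatement |
|---|---|---|---|
| Platelets, 25% | 6.8–7.0 | 10.1–10.7 | 44–57% |
| Platelets, 50% | 13.3 | 16.9–17.7 | 26–32% |
| Platelets, 75% | 19.7–19.8 | 22.0–22.5 | 12–14% |
| Hb, trigger 9.0, 25% | 0.63 | 1.09 | 73% |
| Hb, trigger 9.0, 50% | 1.26 | 1.75 | 39% |
| Hb, trigger 9.0, 75% | 1.87 | 2.18 | 17% |
| Hb, trigger 7.0 (assumed), 25% | 0.62 | 0.79 | 27% |
| Hb, trigger 7.0 (assumed), 50% | 1.25 | 1.46 | 17% |
| Hb, trigger 7.0 (assumed), 75% | 1.88 | 2.02 | 7% |

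The bias was upward in every scenario. With transfusions only at weekly visits, the platelet effect would vanish if day 7 counted as outside.

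**4. Removing the exclusions is no cure.** In the same hemoglobin runs with trigger 9.0, using every measured value gave 1.42, 1.86 and 2.30 g/dL against true 0.63, 1.26 and 1.87, because the transfusion raises the value. The exclusions are sensible. What is missing is a rule for the visits that they empty.

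**The case against.** The strongest reply is that this is one descriptive secondary summary. Section 12.2 sets no significance level. The number of subjects and the median are already part of the standard summary, so shrinkage will be visible. Response rates and transfusion independence are reported separately. The objectives say openly that treatment beyond one year is evaluated in subjects with continuing response. Section 12.5 leaves detail to a plan finalized before database lock. All of this stands and keeps the point modest. But a bare number of subjects does not say why values are missing, and the other endpoints do not correct the mean change.

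Nor are the pre-transfusion data idle. Section 12.1.1.2 counts only transfusions given for stated count thresholds or clinical reasons, and applying that rule needs the recorded count and reason. No analysis, however, uses the count to fill a visit in the change summary.

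A reader might make two stronger inferences. The first is that counts would appear to rise even if nobody improved. The endpoint is within-subject change: with D = 0 the formula in step 2 gives 0 for every k below 8.

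The second is that the bias must be larger in arms with more non-responders and so distort the dose comparison. Take a responder share p, a responder gain of 30 × 10⁹/L and a share u of non-responder visits lost, all assumed. The summarized mean is 30p/(p + (1 − p)(1 − u)). For p = 0.5 (true 15) it is 17.65, 21.43 and 27.27 at u = 0.3, 0.6 and 0.9. For p = 0.25 (true 7.5) it is 9.68, 13.64 and 23.08. The absolute bias is slightly smaller in the lower-response arm at u = 0.3 and 0.6 and larger only at u = 0.9. The difference between arms is 7.97, 7.79 and 4.20 against a true 7.50. Distortion of the dose comparison is possible but not established. From Week 9 doses are also adjusted individually, so later visits are not clean dose comparisons in any case.

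**Conclusion.** The point holds as a worthwhile, inexpensive improvement to a secondary descriptive endpoint. Followed as written, the plan will tend to overstate mean improvement whenever some subjects respond and others remain transfused. The direction follows from the documents' own transfusion triggers and exclusion windows. It would fail only if excluded subjects had changes as large as the rest.

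The effect is strong for hemoglobin, where regularly transfused subjects can be absent throughout. For platelets it is partial and depends on whether day 7 is inside the window. The size cannot be derived from the documents. Under the simulation assumptions it ranged from 12% to 57% for platelets and from 7% to 73% for hemoglobin. The primary endpoint is not touched by this point.

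**What to change.** In section 12.1.1.2, keep the planned summary and add a prespecified companion summary by visit and initial dose group. In it, a scheduled visit inside a post-transfusion window takes the pre-transfusion platelet count or hemoglobin of the most recent transfusion, as recorded under section 6.2.3. State this as an exception both to the scheduled-visit rule in section 12.1.1 and to the no-imputation rule in section 12.4.

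Beside each mean, report the number of subjects excluded for transfusion and the number withdrawn. Label summaries from Week 53 as continuing platelet responders only, citing sections 5.4 and 11.1.1. State whether days 7 and 28 fall inside their windows.

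Ranking subjects as worst because they left under the platelet rules of sections 11.1.1 or 5.4 is not advised. It would score a subject with a real hemoglobin or neutrophil gain as a failure on those measures.

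The cost is SAP wording and a little programming, with no new data collection. The downside is that the companion values may lean low, because they are often the values that triggered the transfusion. The two summaries should therefore be read together as a range, not as one replacing the other.

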Erythroid response is defined in those who with a pretreatment hemoglobin of < 9.0 g/dL as an increase in hemoglobin concentration of ≥ 1.5 g/dL above baseline without transfusion, or reduction in the transfusion unit by at least 4 units for 8 consecutive weeks compared with the pretreatment transfusion requirement in the previous 8 weeks prior to the first administration of AMG531 (Day -55 to Day 1).

Neutrophil Response

Neutrophil response is defined in those with a pretreatment absolute neutrophil count (ANC) of $< 0.5 \times 10^9/L$ as a 100% increase over the baseline, or an increase in ANC of $> 0.5 \times 10^9/L$ in subjects with a pretreatment ANC of $< 1.0 \times 10^9/L$.

Baseline

Baseline values are defined as the values obtained before dosing AMG531 on Study Day 1. Data obtained during the screening period will serve as baseline values for those not measured or reported on Study Day 1. If multiple evaluations are performed during the screening period for a particular test, with the exception of platelet count, the values measured closest to the first administration of AMG531 will be considered as the baseline values (if hemoglobin concentration at Study Day 1 is within 28 days after RBC transfusion, hemoglobin concentration determined during the screening period will be used as baseline hemoglobin).

Baseline Platelet Count

Baseline platelet count is defined as the mean of two lowest platelet counts measured in 8 weeks prior to enrollment. Platelet count that is obtained within 7 days after platelet transfusion will not be used. The baseline platelet according to the definition of protocol Master Ver1.1 (The mean of two lowest platelet counts measured in 8 weeks prior to enrollment. Platelet count that is obtained within 3 days after platelet transfusion will not be used.) will be also collected .

Platelet Transfusion

Platelet transfusion given due to platelet count of $< 10 \times 10^9/L$ (prophylactic transfusion) or due to bleeding (therapeutic transfusion).

RBC Transfusion

RBC transfusion given due to the hemoglobin concentration of ≤ 9.0 g/dL or due to symptomatic anemia

Adverse Drug Reaction

Adverse events of which causal relationship to the investigational product cannot be ruled out (any events assessed to be other than “unlikely” or “not related”).

Study Duration

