Study duration of each subject in this study is specified as the period from the day of obtaining written informed consent through the end of examinations on completion of treatment (or withdrawal).

Observation and Examination Period

In this study, Week 1 (Day 1) is defined to be the day of initial administration of AMG531. Initial dose evaluation period is defined to be the period from Week 1 to Week 8, Extension period is the period from Week 9 to Week 52, and Long-term treatment period is the period from Week 53 to Week 156.

Aplastic Anemia with Refractory Thrombocytopenia

Aplastic anemia with thrombocytopenia defined as platelet count of $\leq 30 \times 10^9/L$ that does not respond to the immunosuppressive therapy (ATG + cyclosporine), or relapsed after having showed response.

Transfusion Independence

Achieving platelet or RBC transfusion free period of at least 8 consecutive weeks.

Tri-lineage response

Tri-lineage response is defined in those achieving platelet response, erythroid response, and neutrophil response all together.

Normal level

Normal level is defined as platelet counts $>50 \times 10^9/L$, hemoglobin concentration >10.0 g/dL, and neutrophil counts $>1.0 \times 10^9/L$

Stable response

Stable response is defined as platelet counts $\geq 30 \times 10^9/L$, hemoglobin concentration ≥ 9.0 g/dL, and neutrophil counts $\geq 0.5 \times 10^9/L$ maintained during dose tapering or discontinuation without transfusion

Cytogenetic abnormality

Any cytogenetic abnormalities newly emerged during or after the initiation of AMG531 treatment

PROTOCOL SYNOPSIS

I TITLE

A phase 2, Randomized, Open-Label, Parallel, Comparative, Dose-Finding Study to Evaluate the Efficacy and Safety of AMG531 in Aplastic Anemia (AA) Subjects with Thrombocytopenia Refractory to Immunosuppressive Therapy

[figure not shown]
II STUDY OBJECTIVES

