5.2 Inclusion criteria

Subjects may be included in the study if they meet all of the following criteria:

- 1) Patients who have provided written informed consent of their free will to participate in this clinical study. Written informed consent must be obtained prior to performing any study-related procedure
- 2) The subject is able and willing to comply with study procedures and follow-up as described in the protocol and ICF
- 3) Males and female subjects ≥ 19 years of age at the time of obtaining informed consent
- 4) Eastern Cooperative Oncology Group (ECOG) performance status (PS) score of ≤ 2 at the time of screening
- 5) Diagnosis of AA, confirmed by bone marrow and cytogenetic studies
- 6) Patient who is refractory to immunosuppressive therapy (IST)
- 7) Prior treatment with at least one course of horse or rabbit anti-thymocyte globulin (ATG) with cyclosporine
- 8) Thrombocytopenia defined as platelet $\leq 30 \times 10^9/L$
- 9) Fulfilling all of the following criteria in the screening examination
 - T-Bilirubin ≤ 1.5 times the upper limit of the laboratory normal range
 - ALT and AST ≤ 3 times the upper limit of the laboratory normal range
 - Creatinine ≤ 2.0 mg/dL

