Tri-lineage response is defined in those achieving platelet response, erythroid response, and neutrophil response all together. The proportion of subjects with tri-lineage response will be calculated in the same manner as the primary variables. Time to tri-lineage response will be summarized.

The proportion of subjects who achieved normal level for 8 consecutive weeks, who started tapering, and who discontinued study drug will be calculated. Time to achieving normal level for 8 consecutive weeks (the initial day of the period), to starting tapering, to discontinuing study drug as a result of tapering will be summarized.

Longest duration of drug discontinuation in subjects while maintaining stable response will be summarized.

Robustness of the results will be evaluated by the analysis calculated in the same manner based on the FAS.

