22 PUBLICATION POLICY

Publication by investigative site of any data from this study must be carried out with prior agreement of the sponsor.

APPENDICES/ATTACHMENTS

Appendix 1

MODIFIED BAUERMEISTER GRADING SCALE FOR RETICULIN*

Grade	Quantification of bone marrow reticulin and collagen
0	No reticulin fibers demonstrable
1	Occasional fine individual fibers and foci of a fine fiber network
2	Fine fiber network throughout most of the section; no coarse fibers
3	Diffuse fiber network with scattered thick coarse fibers but no mature collagen (negative to trichrome staining)
4	Diffuse, often coarse fiber network with areas of collagenization (positive trichrome staining)

* Adopted from Bauermeister, 1971; Bain et al, 2001

Appendix 2

APLASTIC ANEMIA WITH SEVERITY CRITERIA*

Classification	Criteria
Severe	BM cellularity < 25% (or < 50% if < 30% of BM is hematopoietic cells) AND ≥ 2 of the following: 
• Peripheral blood neutrophil count < $0.5 \times 10^9/L$• Peripheral blood platelet count < $20 \times 10^9/L$• Peripheral blood reticulocyte count < $20 \times 10^9/L$
Very severe	As above, but peripheral blood neutrophil count must be < $0.2 \times 10^9/L$
Nonsevere	Hypocellular BM with peripheral blood values not meeting criteria for severe aplastic anemia

* Adopted from Guinan, 2011.

Appendix 3

GIMEMA BLEEDING SCALE*

Grade	Definition
0	No bleeding
1	Petechiae or mucosal bleeding, not requiring intervention
2	Melena, hematemesis, hematuria, hemoptysis
3	Bleeding requiring red blood cell transfusion
4	Retinal bleeding with visual impairment
5	Non-fatal cerebral bleeding
6	Fatal cerebral bleeding
7	Fatal non-cerebral bleeding

* Adopted and modified from Rubella et al., 1997

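### A subject who enters with ANC of 1.0 × 10⁹/L or more can never be a tri-lineage responder, yet stays in the denominator of the tri-lineage proportion

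*Combined protocol and SAP*

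**What the plan says.** **Endpoint.** Definition of Terms and Section 12.1.1.2 both require all three lineages: "Tri-lineage response is defined in those achieving platelet response, erythroid response, and neutrophil response all together".

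**Neutrophil component.** In Definition of Terms, "Neutrophil response is defined in those with a pretreatment absolute neutrophil count (ANC) of" less than 0.5 × 10⁹/L, for whom the ANC must double. The alternative limb asks for a rise of more than 0.5 × 10⁹/L when the pretreatment ANC is below 1.0 × 10⁹/L. Section 12.1.1.2 gives the same two limbs with the same limits.

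**Erythroid component.** Definition of Terms restricts it by starting value: "Erythroid response is defined in those who with a pretreatment hemoglobin of < 9.0 g/dL". Section 12.1.1.2 restates erythroid response without any pretreatment hemoglobin limit.

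**Entry.** Section 5.2 requires platelets of 30 × 10⁹/L or less. No criterion in Sections 5.2 or 5.3 limits ANC or hemoglobin. Severity is recorded at screening but not required, and Appendix 2 includes a nonsevere class: "Hypocellular BM with peripheral blood values not meeting criteria for severe aplastic anemia".

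**Denominator.** Section 12.1.1.2 says: "The proportion of subjects with tri-lineage response will be calculated in the same manner as the primary variables". The primary variable is a proportion of the PPS with a two-sided 95% confidence interval, repeated on the FAS (Section 12.1.1.1). Section 12.1 takes percentages over the total number of subjects. Neither set (Sections 12.6.1 and 12.6.2) carries an ANC or hemoglobin condition, and no evaluable subset is defined.

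**The concern.** The endpoint is gated on a starting value that entry does not require. A subject who enters with an ANC of, say, 1.3 × 10⁹/L fails both neutrophil limbs before the first dose and so cannot be a tri-lineage responder. If that subject is counted in the denominator, the reported proportion mixes two things: how often the drug improves all three lineages, and how many subjects happened to enter without neutropenia.

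In a dose-finding study with four arms of 8, the second element can differ between arms by chance alone, and a difference in attainable ceiling could be taken for a difference between doses. The FAS analysis offers no protection, because it has the same gap.

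**Working it through.** **Inputs from the documents**
- Four dose groups of 8, 4 × 8 = 32, which reproduces the stated target (Section 3.5.1). No response rate, power or significance level is given (Section 12.2), so there is no further planning figure to reproduce.
- Allocation uses the baseline platelet count only (Section 3.4), so the design does not balance ANC.
- The number k of subjects per arm with pretreatment ANC of 1.0 × 10⁹/L or more is not given. I take the share p as 10%, 20% or 30%; this is an assumption.

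**Step 1: can such a subject respond?** The doubling limb needs ANC below 0.5 and the absolute-rise limb needs ANC below 1.0 (× 10⁹/L). At 1.0 or more both are closed, in Definition of Terms and in Section 12.1.1.2 alike. Tri-lineage response needs the neutrophil component, so it is closed too.

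**Step 2: ceiling in an arm of 8.** Highest attainable rate = (8 − k)/8, taking all 8 into the PPS.
- k = 1: 7/8 = 87.5%
- k = 2: 6/8 = 75.0%
- k = 3: 5/8 = 62.5%
- k = 4: 4/8 = 50.0%

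Each such subject costs 1/8 = 12.5 points.

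**Step 3: how likely is at least one in a given arm?** 1 − (1 − p)⁸ = 0.57, 0.83 and 0.94 for p = 10%, 20% and 30%.

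**Step 4: how uneven will the arms be?** Let f(m) be the Binomial(8, p) probability of m such subjects in an arm, with four independent arms. The chance that the largest and smallest counts differ by at most 1 is the sum over m of [f(m) + f(m+1)]⁴ − f(m+1)⁴.
- p = 10%: 0.4157 + 0.0793 + 0.0011 = 0.496, so P(difference of 2 or more) = 0.50
- p = 20%: 0.0515 + 0.1492 + 0.0372 + 0.0014 = 0.239, so 0.76
- p = 30%: 0.0027 + 0.0519 + 0.0877 + 0.0229 + 0.0011 = 0.166, so 0.83

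Two subjects are 2 × 12.5 = 25 points of ceiling.

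**Step 5: effect on a reported figure** (illustrative counts, exact 95% intervals). Suppose half of the subjects who can respond do so.
- k = 2: 3/8 = 37.5% (8.5 to 75.5) over all subjects; 3/6 = 50.0% (11.8 to 88.2) over those able to respond.
- k = 4: 2/8 = 25.0% (3.2 to 65.1) and 2/4 = 50.0% (6.8 to 93.2).

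The underlying rate is the same in both arms. The all-subject figures differ by 12.5 points only because k differs.

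**The case against.** **The denominator is inferred.** No sentence says that subjects outside the ANC limit count as failures. The component definitions are worded for those with a given starting value, which could be read as limiting who is assessed, and Section 12.5 leaves detail to a statistical analysis plan finalised before database lock. This stands in part. But nothing turns that wording into a denominator, and the rules that are written (Section 12.1, and the same-manner instruction in Section 12.1.1.2) lead to all PPS subjects.

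**Hemoglobin.** A reader might infer that subjects with hemoglobin of 9.0 g/dL or more are also certain failures. That follows only from Definition of Terms, and even there it is unclear whether the limit covers the transfusion-reduction limb. Under Section 12.1.1.2 such a subject can still be an erythroid responder. Only the ANC argument holds under both texts. Neutrophil response itself does not depend on hemoglobin at all.

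**Neutrophil proportion.** A reader might extend the point to neutrophil response as reported. The planned endpoint is erythroid and/or neutrophil response. Read as a composite, a subject with a high ANC can still count through the erythroid component, so the certain-failure claim is clear only for tri-lineage response and for any neutrophil proportion shown separately.

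**Normal level.** A subject can reach normal level in all three lineages and still be a tri-lineage non-responder. This is not a contradiction, since response measures a change and normal level a state. Section 12.1.1.2 already reports the proportion reaching normal level for 8 consecutive weeks, with no limit on starting value, so no further proportion is needed.

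**Importance.** The endpoint is secondary and descriptive, with no significance level. It has no fixed time window, and doses may change from Week 9 (Section 6.1.2), so a comparison by initial dose is already blurred. This stands and limits the consequence.

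**Conclusion.** The point holds for ANC and tri-lineage response. Following the plan as written counts a subject with pretreatment ANC of 1.0 × 10⁹/L or more as a tri-lineage non-responder whatever happens on treatment, at a cost of 12.5 points of ceiling per subject in an arm of 8. Uneven spread across arms is likely over the assumed range: a difference of two or more such subjects has probability 0.50 at p = 10% and 0.83 at p = 30%. Those probabilities rest on the assumed p and on independent arms; the ceiling arithmetic does not.

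Whether the same applies to hemoglobin of 9.0 g/dL or more cannot be settled until Definition of Terms and Section 12.1.1.2 are reconciled. A reader might also infer that the choice of dose is compromised. The documents do not support that: the primary endpoint is platelet response at Week 9, which uses neither ANC nor hemoglobin, and it and the sample size are unaffected. The consequence is for the interpretation of one secondary endpoint. It is worth correcting because the remedy is cheap.

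**What to change.** 1. Reconcile the erythroid definition in Definition of Terms with that in Section 12.1.1.2, stating whether a pretreatment hemoglobin limit applies and, if so, whether it covers the transfusion-reduction limb. That limb also needs enough pretreatment transfusion for a fall of 4 units to be possible, so evaluability should be stated for it too.
2. In Section 12.1.1.2, define the evaluable subjects for tri-lineage response as those with pretreatment ANC below 1.0 × 10⁹/L who also meet whatever erythroid pretreatment criterion results from step 1. Use the ANC limit alone for any separate neutrophil proportion.
3. Report the proportion over evaluable subjects beside the all-PPS figure, with the evaluable number per dose group, and do the same for the FAS.

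The cost is SAP wording and table denominators. Baseline ANC and hemoglobin come from the hematology panel already taken at screening and Week 1 (Sections 8.2.1 and 8.2.2), and transfusion history is already recorded (Section 6.2.3). The drawback is smaller denominators and wider intervals: with four evaluable subjects in an arm, 2/4 has an exact 95% interval of 6.8% to 93.2%. For that reason the all-PPS figure should be kept alongside.
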